**Gender**

male       female       other

**Date of birth**

\_\_\_\_\_ (day/month/year)

**Race format**

swiss epic       swiss epic 2 day  
 swiss epic flow       swiss epic 2 day flow

**1. Since how many years do you participate in mountain biking?**

\_\_\_\_\_ Years

**2. On what level do you participate in mountain biking?**

recreational       amateur       elite-amateur       professional

**3. What's your motivation to participate in mountain biking?**

risk       challenge       health factor       fun       beeing outdoors  
 excitement       physical exercise

**4. Rider type**

cross country       trail riding       all mountain       downhill       freeride

**5. Pedal System**

cleat (i.e. Shimano SPD)       platform

**6. Estimated training hours per week in regard to the season**

Spring \_\_\_\_\_ h/Week      Summer \_\_\_\_\_ h/Week      Autumn \_\_\_\_\_ h/Week      Winter \_\_\_\_\_ h/Week

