## **2. Methods**

A survey (as outlined below) of mountain biking related injuries will be conducted on the participants of the Swiss Epic mountain bike event in 2017 held in Valais. The retrospective questionnaire is designed in accordance with existing literature ((Gaulrapp et al., 2001; Lareau and McGinnis, 2011), will include 25 questions and will be translated into English, French, Italian, Spanish and German. The participants will be asked to tick the most appropriate answer. The questionnaire aims to assess the athletes' 1) basic demographics, riding level and years of experience, 2) number of races per year and mean hours of training per week, 3) number and kind of suffered injuries related to mountain biking and medical treatment requirement, 4) and amount and kind of protective gear items.

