## **3. Statistical analysis plan**

Data analyses will be performed using the Statistical Package for Social Sciences (SPSS), version 24.0 (IBM Corporation, Armonk, NY, USA).

Descriptive statistics [means  $\pm$  standard deviations (SD) and relative frequencies (%)] will be retrieved. Pearson correlations will be used to assess correlations between the outcome variables. Chi-squared tests will be applied to determine group differences of injury prevalence and the occurrence of severe, respectively mild injury events. Multivariate logistic regressions will be performed to evaluate predictive factors among the outcome variables (independent variables) of severe injury events (dependent variable; no severe injury = 0 versus severe injury = 1) in elites and amateurs separately. Independent samples t-tests will be used to evaluate mean group differences in demographics, and training and injury related variables between the elite and the amateur mountain bikers. P-values  $< 0.05$  will be considered as statistically significant. According to Cohen (1992), effect sizes will be calculated for the correlation analyses and defined as follows;  $r = 0.20$  small,  $r = 0.50$  medium,  $r = 0.80$  strong.

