**7. How many races per year**

\_\_\_\_\_

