**9. Number of injuries obtained during mountain biking**

\_\_\_\_\_

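### Item 6 asks for weekly training hours without saying which activity counts, so the hours cannot be read as mountain-bike riding time when groups are compared or related to injuries

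*Combined protocol and SAP*

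**What the plan says.** Section 2 (Methods) lists "number of races per year and mean hours of training per week" among the things the survey will assess. Item 6 collects the hours as "Estimated training hours per week in regard to the season", with a separate field for each of four seasons. Neither place names a sport, and training is not defined anywhere.

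The injury count in item 9 is limited to the sport: "Number of injuries obtained during mountain biking". The other items on amount of activity are item 1, "Since how many years do you participate in mountain biking", and item 7, "How many races per year".

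Section 3 (Statistical analysis plan) will use independent samples t-tests to "evaluate mean group differences in demographics, and training and injury related variables between the elite and the amateur mountain bikers". It also plans Pearson correlations among the outcome variables, and logistic regressions for severe injury run within each group. It does not list the predictors by name.

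**The concern.** Two quantities can be meant by training hours: total training load (which may include gym, road or indoor work) and time spent on the mountain bike. Item 6 does not tell the respondent which is wanted. One rider may report all training. Another may report only mountain-bike sessions. A third, who rides for enjoyment, may leave out rides that do not feel like training.

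If the reading varies with rider level, a difference in mean hours between elites and amateurs is partly a difference in how the item was understood. If the reading varies within a group, a link between hours and injury is blurred, because off-bike hours carry no risk of a mountain-biking injury. Adjusting for the same hours does not help, since the adjustment variable is the one that is unclear.

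**Working it through.** The documents give no expected hours, standard deviation or sample size, so there is no planned figure to reproduce. The check is of wording first, then an illustration on assumed values.

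**Wording, side by side**

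- Items 1, 2 and 3 name mountain biking, and item 9 limits injuries to it.
- Item 6 and the matching phrase in Section 2 do not name it. Nor do items 4, 5, 7 and 8, so silence alone is not unusual on this form.
- Item 6 differs in that the missing information changes the number reported. Rider type and pedal system have an obvious referent on a mountain-biking form; training hours do not, because athletes also train off the bike.
- Years of participation (item 1) and races per year (item 7) are the only other volume items. Neither can be converted into weekly mountain-bike hours.

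**Effect on the t-test (assumed values, illustration only)**

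Assume true riding of 8 h/week in both groups, SD 4, two-sided alpha 0.05. Let elites misreport by a share a and amateurs by a share b. The recorded difference is 8(1 + a) - 8(1 + b).

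| a (elite) | b (amateur) | Recorded difference, h/week |
|---|---|---|
| 0 | 0 | 0 |
| +10% | +10% | 8.8 - 8.8 = 0 |
| +10% | 0 | 8.8 - 8.0 = 0.8 |
| 0 | +10% | 8.0 - 8.8 = -0.8 |
| +10% | -10% | 8.8 - 7.2 = 1.6 |
| -10% | +10% | 7.2 - 8.8 = -1.6 |

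The chance that such a spurious difference d is declared significant in its own direction is approximately Phi(|d| / (4 × sqrt(2/n)) - 1.96), with n per group:

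- |d| = 0.8: 0.12, 0.17 and 0.29 at n = 30, 50 and 100.
- |d| = 1.6: 0.34, 0.52 and 0.81 at the same n. For n = 50: 1.6 / (4 × sqrt(2/50)) = 2.00, and Phi(2.00 - 1.96) = 0.52.
- d = 0: 0.025 in each direction, the nominal rate.

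**Effect on a within-group correlation (assumed values)**

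If the variation in reading acts as random error, the observed correlation is r × sqrt(reliability). A true r of 0.30 becomes 0.285, 0.251 and 0.212 at reliabilities of 0.9, 0.7 and 0.5. If the off-bike share is itself related to injury, the error is not random and this formula does not bound it.

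**The case against.** The strongest reply is that context supplies the sport. The form's title names mountain biking, item 6 follows five items on mountain-biking participation and equipment, and several neighbouring items also leave the sport unstated. Section 2 asks for training hours and item 6 collects training hours, so item and objective agree. Total training load is a legitimate descriptor of an athlete, and the stated aim is descriptive.

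Much of this stands. Some respondents, perhaps most, will count only mountain biking, and a t-test on self-reported training is valid as a comparison of just that. What remains is that the title does not tell a leisure rider whether to count leisure rides, and the documents do not say that total load is intended. Nor could an analyst find out afterwards which reading each respondent used.

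A reader might infer more than the documents support, in three ways:

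- **That errors run in opposite directions, inflating elite hours and deflating amateur hours.** Item 2 has four levels, including recreational, and Section 3 does not map them to elite and amateur. Respondents are entrants in a race event, so riders who do not regard their riding as training may be uncommon. Amateurs may also train off the bike, which would push both groups the same way.
- **That an injury rate per hour is biased by some calculable factor.** Section 3 plans no rate per hour, so no planned estimate carries such a factor.
- **That between-group error distorts the regressions.** These are run within each group, so a group-level shift does not act inside them. There the risks are attenuation, confounding by the off-bike share, and coefficients that cannot be compared across groups, and only if hours are entered as a predictor.

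**Conclusion.** The point holds as an ambiguity in one item that cannot be repaired after collection. It is not a demonstrated bias. Item 6 leaves unclear whether off-bike training and leisure mountain-bike rides count, while the injuries it may be related to are limited to mountain biking. The t-test on training variables is the most exposed analysis. Correlations and regressions are affected only so far as they use hours.

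The documents do not fix the size or direction of the error. In the illustration a 10% misreading gives anything from -1.6 to +1.6 h/week, with no distortion at all if both groups read the item alike. Those figures rest on assumed equal true riding of 8 h/week and SD 4, and show sensitivity only. Because the remedy is cheap and keeps the training variable that Section 2 wants, the change is worth making.

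**What to change.** Split item 6 into two lines, each with the same four seasonal fields:

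- (a) hours per week riding a mountain bike (training, leisure and racing together);
- (b) other training hours per week.

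Report both, or their sum, as training load. Use (a) wherever hours are related to mountain-biking injuries. Reword Section 2 to name the two quantities, and state in Section 3 which one enters each analysis.

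The cost is one extra line in each of the five language versions, and slightly less direct comparability with surveys that asked only for total training hours.

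If data are already collected, label the variable self-defined training hours in tables and text, and do not interpret it as riding exposure.

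This change does not by itself give a valid injury rate. Item 9 has no time window and item 6 has no reference year, so even clean riding hours would not cover the same period as the injuries.

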**7. How many races per year**

\_\_\_\_\_

**8. Protective gear**

helmet       gloves       eyewear       upper armour       lower armour

other \_\_\_\_\_

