**11. Mechanism of injury**

loss of control       loss of traction       collision with object       collision with rider       mechanical problem  
 unknown       other \_\_\_\_\_

**12. Severity of injury** (if more than one injury occurred, choose the most severe one)

no medical treatment needed     self-administered medical treatment     MD administrated medical treatment     Medical treatment in ER     Overnight hospitalization

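### Protective gear is recorded without a time frame and is not tied to the graded injury, so gear taken up after a severe injury could distort the severe-injury regression

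*Combined protocol and SAP*

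**What the plan says.** - **Gear.** Section 2 (Methods) lists "amount and kind of protective gear items" as part of the fourth domain that the questionnaire assesses. On the form this is item 8, "8. Protective gear", with boxes for helmet, gloves, eyewear, upper armour, lower armour and other. The item has no verb, no time frame and no reference to an injury. It stands among the items on riding habits (years, level, rider type, pedals, training, races), ahead of all the injury items.
- **Injury.** Item 12 grades severity, and riders with several injuries are told: "if more than one injury occurred, choose the most severe one". There is no look-back limit. Item 10 asks for the time since the most recent injury, which need not be the most severe one.
- **Model.** Section 3 (Statistical analysis plan) plans logistic regressions to find "predictive factors among the outcome variables (independent variables) of severe injury events", coded "no severe injury = 0 versus severe injury = 1", run "in elites and amateurs separately". Gear is not named as a predictor, and nothing excludes it. The section says nothing about the order of exposure and injury.
- **Tick rule.** The form's introduction asks for a single answer per question, although gear items are worn together.

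**The concern.** The dependent variable is a past event that may be years old. The gear answer has no date, and from its position on the form many riders will probably answer for what they wear now. A rider who bought armour because of a bad crash would then count as an armour wearer with a severe injury. The exposure would have followed the outcome, but the model would read it as a predictor.

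The form's introduction tells riders that the survey may help prevent injury, so readers are likely to take a gear coefficient as safety information. If post-injury uptake is mixed into it, a protective item could appear neutral or harmful. No item records when gear was adopted or what was worn at the graded injury, so no later analysis of these data can repair this.

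**Working it through.** **What there is to reproduce.** The documents give no sample size, event count, gear prevalence, uptake rate or odds ratio. There is no figure of the plan's own to check, and every rate below is an assumption.

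**Assumed inputs**
- p0 = 0.20: share wearing armour at the relevant time among riders without a severe injury (odds 0.25).
- True OR: 1.0 (no effect) or 0.5 (odds of severe injury halved).
- u_s = 10%, 20% or 30%: share of non-wearers who take up armour after a severe injury.
- u_n = 0%, 5% or 10%: share of non-wearers who take it up among other riders.

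**Formulas**
- p1 = o/(1 + o), with o = true OR × p0/(1 − p0).
- Reported use = p + (1 − p) × u, using p1 and u_s for severe cases and p0 and u_n for the others.
- Apparent OR = odds of reported use in severe cases ÷ odds of reported use in the others.

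**Worked example (u_s = 20%, u_n = 0)**
- True OR 1.0: p1 = 0.20, reported use 0.20 + 0.80 × 0.20 = 0.36, odds 0.5625, apparent OR 0.5625/0.25 = 2.25.
- True OR 0.5: o = 0.125, p1 = 0.111, reported use 0.111 + 0.889 × 0.20 = 0.289, odds 0.406, apparent OR 0.406/0.25 = 1.62.

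**Results (p0 = 20%, crude OR)**

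| Uptake after severe injury | Uptake in others | True OR 1.0 appears as | True OR 0.5 appears as |
|---|---|---|---|
| 10% | 0% | 1.56 | 1.00 |
| 20% | 0% | 2.25 | 1.62 |
| 30% | 0% | 3.14 | 2.43 |
| 10% | 5% | 1.23 | 0.79 |
| 20% | 5% | 1.78 | 1.29 |
| 30% | 5% | 2.49 | 1.92 |
| 20% | 10% | 1.45 | 1.04 |
| 10% | 10% | 1.00 | 0.64 |

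**Point at which protection disappears.** With 5% uptake in the others, their reported use is 0.20 + 0.80 × 0.05 = 0.24. The apparent OR reaches 1 when u_s = (0.24 − p1)/(1 − p1). For a true OR of 0.5 this is (0.24 − 0.111)/0.889 = 14.5%. For a true OR of 0.7 (p1 = 0.149) it is (0.24 − 0.149)/0.851 = 10.7%.

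**Opposite direction.** If 10% of severely injured wearers stop wearing armour and nobody takes it up, reported use in cases is 0.20 × 0.90 = 0.18. With a true OR of 1.0 the apparent OR is (0.18/0.82)/0.25 = 0.88, so gear with no effect looks protective.

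**With gear asked as worn at the graded injury.** Both uptake terms are zero, and the crude OR equals the true OR under these assumptions. Confounding and recall error remain.

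**The case against.** Four objections carry weight.

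1. **The form does not ask for current use.** A reader might infer that it does from the position of item 8 among habit items. The item states no tense at all, and riders may answer for now, for this race or in general. The defect is the missing time frame. Current use is only the likely reading.
2. **Gear need not come out as harmful.** A reader might infer that it must. That needs uptake clearly higher after severe injury than in the comparison group. That group may include riders with milder injuries, who may also adopt gear. Equal uptake only dilutes the association, and abandoning gear biases it the other way. Figures that assume no uptake in the others are the unfavourable end of the range.
3. **Gear is not a named predictor.** It enters only through the general wording on the assessed variables, and the Introduction describes the study's aim as descriptive. Its inclusion is probable, not specified.
4. **The odds ratios are crude.** The plan is a multivariable model fitted separately in two groups, so its coefficients could differ from those in the table.

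These points limit the claim but do not remove it. Gear is eligible for the model, no item fixes its timing, and adjustment for other variables cannot restore the order of gear and injury. An unknown direction of bias also leaves the gear coefficient uninterpretable.

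Pedal system (item 5) lacks a time frame as well. Nothing in the documents suggests that riders change pedals after an injury, so the argument is weaker there.

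**Conclusion.** The concern holds as a possible distortion of unknown direction. The plan as written allows a gear coefficient for severe injury that mixes gear worn at the injury with gear adopted or dropped afterwards, and the data cannot separate the two.

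With 20% use at the time of injury and 10–30% uptake after severe injury, a true OR of 1.0 appears as 1.56–3.14 if other riders take up none, and as 1.23–2.49 if 5% of their non-wearers do. For a true OR of 0.5 the ranges are 1.00–2.43 and 0.79–1.92. Prevalence and uptake are both assumed, so these figures show sensitivity and do not predict the study's result. The descriptive aim of the survey is not affected.

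**What to change.** **If the form can still be changed**
- Reword item 8 to ask for *gear you usually wear now*.
- Directly after item 12, add a line with the same list, marked *tick all that apply*: *gear worn at the time of this most severe injury*. It must name the injury graded in item 12, because item 10 concerns the most recent one. It must also override the single-answer instruction in the form's introduction.
- State in Section 3 that only the at-injury answers serve as gear predictors, comparing severe with non-severe injuries among injured riders, and that usual gear is reported descriptively.
- Asking for the pedal system at the time of that injury is optional.

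**If the form is fixed.** State in Section 3 that item 8 is left out of the severe-injury regression and reported descriptively. This needs no new data.

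**Cost.** One extra line in five languages, and some recall error for old injuries. The estimate would apply only to severity given an injury. Gear may also affect whether an injury occurs, so restricting to injured riders can itself introduce selection, and the report should say so.

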**9. Number of injuries obtained during mountain biking**

\_\_\_\_\_

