**10. How long ago was your most recent injury?**

\_\_\_\_\_ /months

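### Item 9 sets no recall window and the analysis plan states no exposure adjustment, so the elite–amateur comparison of injury counts may mix years of riding and recall with risk

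*Combined protocol and SAP*

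**What the plan says.** Section 2 (Methods) describes the survey as retrospective: "The retrospective questionnaire is designed in accordance with existing literature". The items that bear on injury frequency are these.

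- **Item 9:** "Number of injuries obtained during mountain biking", an open number with no period and no definition of injury.
- **Item 1:** "Since how many years do you participate in mountain biking", an open number of years.
- **Item 10:** "How long ago was your most recent injury", answered in months, for the latest injury only.
- **Item 6:** "Estimated training hours per week in regard to the season", one figure for each of four seasons. Item 7 asks for races per year.
- **Item 12:** one severity rating, with the instruction "if more than one injury occurred, choose the most severe one", again with no period.
- **Item 2:** "On what level do you participate in mountain biking", with four self-rated levels.

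Section 3 plans independent-samples t-tests of training and injury variables between elite and amateur riders. It also plans chi-squared tests of injury prevalence and severity, Pearson correlations among the variables, and logistic models of severe injury within each level. For the comparisons of count and prevalence it states no rate, offset or adjustment for time at risk. It does not name the predictors in the logistic models.

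**The concern.** A count with no period grows with the time over which it accumulates. Two riders with the same yearly risk will report different totals if one has ridden longer. If mean years of riding differ between elite and amateur riders, an unadjusted t-test on the total can show a difference that is not one of risk, or hide one that is. The proportion ever injured behaves in the same way.

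Recall adds a second distortion. Older injuries are more likely to be forgotten, so the share of the true total that is reported falls as years of riding rise. Dividing the total by item 1 years would deal with time at risk but not with recall.

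The exposure items do not match the count either. Items 6 and 7 are framed by season and by year, with no career history, so correlating them with a career total mixes two periods. The number and kind of injuries is one of the four things section 2 sets out to assess, so this is a core variable. The survey is anonymous, so a missing period cannot be recovered by follow-up.

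**Working it through.** **No figure to reproduce.** The documents give no sample size, injury rate, recall accuracy or distribution of years of riding. What follows is an illustration under stated assumptions.

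**Assumptions (none from the documents).** The true injury rate is constant and the same for all riders. Injuries are forgotten at a continuous rate f = 0.05, 0.10 or 0.15 a year. Riders with T = 5 and T = 15 years are compared.

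**Formulas.**
- Share of the true total recalled: S(T) = (1 − exp(−fT)) / (fT).
- Apparent per-year rate ratio, 15 v 5 years: S(15) / S(5).
- Reported raw-count ratio, 15 v 5 years: (15/5) × S(15) / S(5).

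| f | S(5) | S(15) | Per-year ratio | Raw-count ratio |
|---|---|---|---|---|
| 0 | 1.00 | 1.00 | 1.00 | 3.0 |
| 0.05 | 0.88 | 0.70 | 0.80 | 2.4 |
| 0.10 | 0.79 | 0.52 | 0.66 | 2.0 |
| 0.15 | 0.70 | 0.40 | 0.57 | 1.7 |

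For f = 0.10: S(5) = (1 − exp(−0.5))/0.5 = 0.79, S(15) = (1 − exp(−1.5))/1.5 = 0.52, their ratio is 0.66, and 3 × 0.66 = 2.0.

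The raw count therefore makes the experienced rider look worse (1.7 to 2.4 times), and forgetting pulls that ratio down from 3.0. The per-year rate makes the same rider look better (20–43% lower).

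**From riders to levels.** The same model was run with an annual forgetting proportion d of 2–20%, so that L = −ln(1 − d) replaces f. The mean years for each level are assumed.

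| Amateur / elite years | Raw ratio elite/amateur, perfect recall | Raw ratio, d = 2–20% | Per-year ratio, d = 2–20% |
|---|---|---|---|
| 8 / 15 | 1.88 | 1.75 to 1.16 | 0.93 to 0.62 |
| 10 / 10 | 1.00 | 1.00 | 1.00 |
| 15 / 10 | 0.67 | 0.70 to 0.93 | 1.05 to 1.39 |

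The direction depends on which level has ridden longer. With equal years there is no bias between levels. In both unequal cases the raw ratio stays on the side set by riding time, so forgetting offsets it only in part.

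**With a common 12-month window.** At d = 2, 5, 10 and 20% the recalled share is 99.0%, 97.5%, 94.9% and 89.6% for every rider. With equal true rates the elite/amateur ratio is then 1.00 whatever the years of riding. This needs at least 12 months of riding and the same forgetting rate in both levels.

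**What item 10 gives.** A rider whose latest injury was 12 months ago or less was injured in that window. Twelve-month prevalence is thus available from the present form. The number of injuries in that window is not.

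**The case against.** The strongest reply is that the study is descriptive and a career total is a legitimate description. The form is said to follow existing literature, which cannot be judged from the documents. That protects the career count as a summary. It does not protect a significance test of that count between levels without regard to time at risk.

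Four stronger readings are tempting, and the documents do not support them.

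- *The missing window makes experienced riders look safer.* That holds only for a count divided by years, which section 3 does not plan. On the raw count the same model points the other way.
- *The comparison between levels is biased.* No section gives years of riding by level, and the grouping of the four item 2 levels into elite and amateur is not stated. Bias is possible, not shown.
- *The count spans some particular range of years, such as one to twenty or more.* Item 1 is an open field with no stated range.
- *Nothing about the last 12 months can be recovered.* Item 10 gives the prevalence; only the count is lost.

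The forgetting rate is also open to challenge. At 2% a year a 20-year rider still recalls 82% of injuries. One rate for all injuries is crude, because item 12 runs from "no medical treatment needed" to an overnight hospital stay. Lower forgetting, however, moves the raw-count ratio towards 3.0, so this weakens the recall argument and not the one about riding time.

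Finally, a 12-month sub-count alone would leave item 12 without a window and injury undefined. The first of these is taken up in the fix.

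**Conclusion.** The point holds in a limited form. Item 9 is a career total from memory, and the plan compares injury variables between levels with no stated adjustment for years or hours of riding. If years of riding differ between levels, the comparison may be biased, in a direction the documents do not determine.

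Unequal riding time is the main mechanism on the planned raw count; forgetting partly offsets it. The size (1.7 to 2.4 times on the raw count, 20–43% lower per year) is for 15 against 5 years of riding. It rests on equal true rates and an assumed 5–15% forgetting a year. It is not an estimate of the difference between elite and amateur riders. A reader should not infer that experienced riders will appear to have fewer injuries in the planned analysis.

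This is a cheap improvement that should be made, not a fault that defeats the survey.

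**What to change.** 1. Add one line to item 9: *of these, how many in the last 12 months?*
2. Use that count for the elite–amateur comparison of injury rates, with item 6 hours as exposure, for example in a Poisson or negative binomial model with an offset for the log of hours. State that the t-test is not used for this comparison.
3. For the chi-squared test of prevalence, define injured as a latest injury 12 months ago or less (item 10). This needs no change to the form.
4. Keep the career count as description. If it is compared between levels, adjust for item 1 years and say that this does not correct for recall.
5. Item 12 has no window either, and the chance of ever having had a severe injury rises with years ridden. Name item 1 years as a covariate in the severe-injury logistic models.

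**Cost.** The form gains one line in five languages. Fewer injuries fall in a 12-month window, so the rate comparison is less precise; the career total is still collected. Steps 3 to 5 change only the analysis text and remain possible if the form can no longer be altered.
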